“Table 6.2.4 Summary of DAS28-4CRP by each Visit per Baseline MTX Dose”

Analysis object: Patients included in the efficacy analysis set (DAS28-4CRP)

Purpose of analysis: To indicate the number of patients by evaluation time, and summary statistics of the score and response for the DAS28-4CRP score by the group of MTX dose at the start of Humira treatment.

In addition, paired t tests should be performed for the response from the start of treatment, and the results of intergroup comparison by analysis of variance should be calculated by evaluation time.

Note: The group separation should follow the concomitant MTX dose (mg/week) in the patient background in “11. Data-layer separation.”

This form should be prepared only at the time of literature analysis.

“Table 6.2.5 Summary of DAS28-4CRP by each Visit per Average Usage MTX Dose of up to week 52”

Analysis object: Patients included in the efficacy analysis set (DAS28-4CRP)

Purpose of analysis: To indicate the number of patients by evaluation time, and summary statistics of the score and response for the DAS28-4CRP score by two groups of the mean MTX dose at week 52: < 12.0 mg/week group or ≥ 12.0 mg/week group. In addition, paired t tests should be performed for the response from baseline, and the results of intergroup comparison by analysis of variance should be calculated by evaluation time.

Note: It should be categorized by the following two categories based on the increase and decrease of the mean MTX dose from the start of Humira treatment to week 52: “< 12.0” and “12.0 \leq .”

This form should be prepared only at the time of literature analysis.

“Table 6.2.6 Univariate logistic analysis event: DAS28-4CRP ≤ 2.6 at week 104”

Analysis object: Patients included in the efficacy analysis set (DAS28-4CRP)

Purpose of analysis: To conduct univariate logistic regression analysis with the number of patients meeting the week 104 DAS28-4CRP < 2.6 as the objective variable and each patient background factor as the explanatory variable, and to indicate the number of patients analyzed, number of patients who developed ADRs, incidence rate, odds ratio, CI and p values.

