Purpose of analysis: To indicate the correlation with the patient background items for the patients who achieved mTSS change below 0.5 at week 52. Patient background items and categories are shown below.

<Patient background item>	<Included data>
Consultation category	Outpatient, inpatient
Gender	Male, female
Age	Continuous value
Age category 1	Aged < 15, 15<= <30, 30<= <50, 50<= <65, 65 <= < 75, 75<= < 85, <= 85
Age category 2	Aged < 15, 15 <= <65, <=65
Weight	Continuous value
Weight category	< 30, 30<= <40, 40<= <50, 50<= <60, <=60
Duration of illness	Continuous value
Category of duration of illness	< 3, 3<= <6, <=6
Complication	Present, absent
Smoking history	Present, absent
RA stage/progression	Stage I, Stage II, Stage III, Stage IV
Disability level of RA	Class I, Class II, Class III, Class IV
Past history	Present, absent
History of allergy	Present, absent
MTX at treatment start	<=12.0 <14.0, <=14.0 <16.0, <=16.0
DMARDs at treatment start (excluding MTX)	Present, absent
Adrenocortical hormones at treatment start	Present, absent
DMARDs during treatment	Present, absent
Adrenocortical hormones during treatment	Present, absent
Other concomitant drugs during treatment	Present, absent

DAS-28CRP at treatment start	Continuous value
Category of DAS-28CRP at treatment start	<2.6,2.6<=

Note: To indicate Spearman rank correlation coefficient and its p value should be indicated for correlation coefficient.

This form should be prepared only at the time of literature analysis.

“Table 6.9.4.2 Correlation of Subjective background (Spearman's rank correlation coefficient) at the mTSS Remission by Week 104”

Analysis object: Patients included in the efficacy analysis set (mTSS at week 104)

Purpose of analysis: To indicate the correlation with the patient background items for the patients who achieved mTSS change below 0.5 at week 104 by using the same technique as Table 6.9.4.1.

“Table 6.9.5.1 Univariate logistic analysis event: ≤ 0.5 delta mTSS at 52 week”

Analysis object: Patients included in the efficacy analysis set (mTSS at week 52)

Purpose of analysis: To conduct univariate logistic regression analysis with the number of patients meeting the week-52 mTSS change ≤ 0.5 as the objective variable and each patient background factor as the explanatory variable, and to indicate the number of patients analyzed, number of patients who developed ADRs, incidence rate, odds ratio, CI and p values.

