To handle the followings as the category data: [consultation category (outpatient, inpatient)], [gender (male, female)], [age category (< 15 , ≥ 15 and < 30 , ≥ 30 and < 50 , ≥ 50 and < 65 , and ≥ 65 and < 75 , ≥ 75 and < 85 , ≥ 85)], [age category: (< 15 , ≥ 15 and < 65 , ≥ 65)], [weight category (< 30 , ≥ 30 and < 40 , ≥ 40 and < 50 , ≥ 50 and < 60 , ≥ 60)], [category for duration of illness (< 3 months, ≥ 3 months and < 6 months, ≥ 6 months)], [complication (present, absent)], [smoking history (absent, present)], [RA stage/progression (Stage I/Stage II, Stage III/Stage IV)], [RA disability level (Class I/Class II, Class III/Class IV)], [past history (absent, present)], [history of allergy (absent, present)], [MTX at treatment start (≥ 12.0 mg/week and < 14.0 mg/week, ≥ 14.0 mg/week and < 16.0 mg/week, ≥ 16.0 mg/week)], [DMARDs at treatment start (excluding MTX) (absent, present)], [adrenocortical hormones at treatment start (absent, present)], [DMARDs during treatment (absent, present)], [adrenocortical hormones during treatment (absent, present)], [other concomitant drugs during treatment (absent, present)], [DAS28-4CRP at treatment start (< 2.6 , $2.6 \leq$)]; and also indicate the results for [age], [weight], [duration of illness] and [DAS28-4CRP at treatment start] as the quantitative data.

Note: This form should be prepared only at the time of literature analysis.

“Table 6.9.5.2 Univariate logistic analysis event: ≤ 0.5 delta mTSS at 104 week”

Analysis object: Patients included in the efficacy analysis set (mTSS at week 104)

Purpose of analysis: To tabulate the number of patients satisfying week 104 mTSS change below 0.5 as the objective variance by using the same technique as Table 6.9.5.1.

“Table 6.9.6.1 Multivariate logistic analysis event: ≤ 0.5 delta mTSS at 52 week”

Analysis object: Patients included in the efficacy analysis set (mTSS at week 52)

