Purpose of analysis: To conduct multivariate logistic regression analysis with the number of patients meeting the week 52 mTSS change ≤ 0.5 as the objective variable and each patient background factor as the explanatory variable, and to indicate the number of patients analyzed, number of patients who developed ADRs, incidence rate, odds ratio, CI and p values. [Gender (male, female)], [complication (absence, presence)] and [progression (Stage I/Stage II, Stage III/Stage IV)] should be handled as categorical data for the patient background factors, and the results should be indicated as the quantitative data for [duration of illness].

Note: This form should be prepared only at the time of literature analysis.

“Table 6.9.6.2 Multivariate logistic analysis event: ≤ 0.5 delta mTSS at 104 week”

Analysis object: Patients included in the efficacy analysis set (mTSS at week 104)

Purpose of analysis: To tabulate the number of patients satisfying week 104 mTSS change below 0.5 as the objective variance by using the same technique as Table 6.9.6.2.

“Table 6.10.1 Percentage of patients without a trend or worsening of the bone erosion score (evaluation time at week 52)”

Analysis object: Patients included in the efficacy analysis set (mTSS at week 52)

Purpose of analysis: To indicate the number of patients and summary statistics of the score and response by evaluation time for the bone erosion score and conduct a paired t test for the response from baseline.

Additionally, the number and percentage of the patients by evaluation time by the category of the bone erosion score should be shown.

The category of the bone erosion score should follow “11. Data-layer separation.”

Note: None in particular.

“Table 6.10.2 Percentage of patients without a trend or worsening of bone erosion score (evaluation time at week 104)”

Analysis object: Patients included in the efficacy analysis set (mTSS at week 104)

Purpose of analysis: To tabulate the patients included in the efficacy analysis set (mTSS at week 104) by using the same tabulation technique as Table 6.10.1.

Note: None in particular.

“Table 6.11.1 Percentage of patients without a trend or worsening of the joint space narrowing score (evaluation time at week 52)”

Analysis object: Patients included in the efficacy analysis set (mTSS at week 52)

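### The efficacy logistic regression tables are told to print adverse drug reaction counts and rates beside odds ratios for remission or structural non-progression

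*SAP*

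**What the plan says.** All the relevant text is in SAP 13.3.

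- **Table 6.2.6.** The title reads "Univariate logistic analysis event: DAS28-4CRP ≤ 2.6 at week 104". The body specifies "univariate logistic regression analysis with the number of patients meeting the week 104 DAS28-4CRP < 2.6 as the objective variable", with each background factor as explanatory variable. The output requested is "number of patients analyzed, number of patients who developed ADRs, incidence rate, odds ratio, CI and p values".
- **Table 6.9.5.1** (univariate, week 52). The outcome is the "number of patients meeting the week-52 mTSS change ≤ 0.5 as the objective variable". The output list is the same and includes the "number of patients who developed ADRs, incidence rate, odds ratio, CI and p values".
- **Table 6.9.6.1** (multivariate, week 52). The outcome is the "number of patients meeting the week 52 mTSS change ≤ 0.5 as the objective variable", with the same output list again.
- **Table 6.9.5.2** (univariate, week 104) is to be produced "by using the same technique as Table 6.9.5.1".
- **Table 6.9.6.2** (multivariate, week 104) is to be produced "by using the same technique as Table 6.9.6.2", which is its own number.

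SAP section 2 defines an ADR as an adverse event for which a causal link with Humira cannot be excluded. Section 10.2 derives the variable in the same sense. Nothing in section 13.3 gives the term another meaning for these tables.

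**The concern.** In a logistic regression table, the number analysed, the number with the event and the event rate let a reader see what an odds ratio rests on. Here the event is remission or structural non-progression, but the count and rate requested belong to drug reactions.

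The instruction can be executed. ADRs are a derived variable, and Table 5.4 already tabulates them by background factor, so a programmer following the text would get output that runs cleanly. The reader would then have odds ratios for one outcome beside counts for another. The odds ratios could not be checked against the counts, and levels with few or no efficacy events would not show. The number analysed would still be correct, so empty levels would remain visible.

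The protocol synopsis also says that the influence of the regression variables on treatment success will be illustrated by stratified groups. ADR counts by stratum do not do that.

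**Working it through.** The plan states no figure for these columns, so there is none to reproduce. The check is to compare the modelled outcome with the requested count, table by table.

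| Table | Modelled event (body text) | Event in title | Count and rate requested |
|---|---|---|---|
| 6.2.6 | DAS28-4CRP < 2.6, week 104 | ≤ 2.6 | ADRs |
| 6.9.5.1 | mTSS change ≤ 0.5, week 52 | ≤ 0.5 | ADRs |
| 6.9.5.2 | mTSS change below 0.5, week 104 | ≤ 0.5 | ADRs, inherited from 6.9.5.1 |
| 6.9.6.1 | mTSS change ≤ 0.5, week 52 | ≤ 0.5 | ADRs |
| 6.9.6.2 | mTSS change below 0.5, week 104 | ≤ 0.5 | apparently ADRs; the text cites itself, and 6.9.6.1 is presumably meant |

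**Extent.** The univariate list has 19 categorical factors: 14 with two levels, three with three levels (coarse age, duration of illness, MTX dose), one with five (weight) and one with seven (fine age). That is 14×2 + 3×3 + 5 + 7 = 49 levels in each univariate table. Four quantitative variables are added. The multivariate tables use three two-level factors (6 levels) and one quantitative variable.

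**Are the right counts available elsewhere?**

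- Table 6.2 gives remission by visit, without background factors.
- Tables 6.9.1.x and 6.9.3.x give mTSS change categories, without background factors.
- Table 6.8.1 is by background factor, but reports EULAR response at the final evaluation, which is a different outcome and time.
- Listing 8.1 gives DAS28-4CRP scores at weeks 52 and 104 and a flag for mTSS change ≤ 0.5, patient by patient with background information. The counts could be rebuilt from it after restricting to the right analysis set, since the listing covers all patients with fixed CRFs.

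So no summary table supplies them; one patient listing would allow them to be reconstructed.

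**Illustration with assumed counts.** None of these counts is in the documents. Take two levels of 85 and 86 patients. If 51 and 43 are in remission, the modelled odds ratio is (51/34)/(43/43) = 1.50. If the columns beside it show 26 patients with ADRs in each level, they imply (26/59)/(26/60) = 1.02. The odds ratio of 1.50 is correct, but the printed counts cannot confirm it.

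**Cut-offs.** SAP section 11 defines DAS28-4CRP remission as < 2.6, so the body of Table 6.2.6 is consistent and its title is not. For mTSS, section 11 and Listing 8.1 use ≤ 0.5. Section 10.3 takes mTSS as the mean of two readers, so a change of exactly 0.5 can occur. The inequality therefore decides whether such a patient counts as an event.

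**The case against.** The strongest reply is that this is a translation or copying slip with little consequence. Every title names an efficacy event, every body states an efficacy outcome, and the odds ratios, intervals and p values are specified on that outcome. The SAP has similar slips: Table 5.3.1 asks for an ADR total while describing adverse events, and Table 6.2 refers to the ESR category in a CRP table. Tables 6.2.6, 6.9.5.1 and 6.9.6.1 are prepared only for the literature analysis. SAP 14.1 points to a separate output plan, so the final column labels are unknown. All of that stands and keeps the point minor. It does not make the instruction right.

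Two stronger readings are tempting, and the documents do not support them.

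- *A reader might infer that the error would go unnoticed.* A column labelled as ADRs in an efficacy table would look out of place. Its totals would generally disagree with Tables 6.2, 6.9.1.x and 6.9.3.x, and Listing 8.1 allows the counts to be rebuilt. An ADR rate would be read as a remission rate only if the label were also lost.
- *A reader might infer a definite size of error in the printed rates.* The documents give no ADR incidence. The 55% remission figure is a week 52 planning value for DAS28, whereas Table 6.2.6 is at week 104. No expected non-progression rate is given for the mTSS tables. The discrepancy cannot be put in percentage points.

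**Conclusion.** The point holds as an output specification error. Three tables (6.2.6, 6.9.5.1, 6.9.6.1) ask in so many words for the count and rate of the wrong outcome. A fourth (6.9.5.2) inherits this, and a fifth (6.9.6.2) does if its self-reference is meant for Table 6.9.6.1. The effect is confined to the count and rate columns. Model estimates and the primary endpoint are unaffected.

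Severity is minor: these are secondary tables, and the slip is probably one of wording. It still merits correction, because the phrase is an operative programming instruction and no other summary table gives the event counts by factor level. The conclusion assumes that ADR carries its SAP definition here, and that the separate output plan, which is not among the documents, does not already override the text.

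**What to change.** 1. **Table 6.2.6:** replace the ADR count and incidence with the number and percentage of patients with DAS28-4CRP < 2.6 at week 104, for each factor level. Change the title from ≤ 2.6 to < 2.6 to match section 11.
2. **Tables 6.9.5.1 and 6.9.6.1:** replace the phrase with the number and percentage of patients with mTSS change ≤ 0.5 at week 52, for each factor level.
3. **Tables 6.9.5.2 and 6.9.6.2:** state the same columns for week 104, and change the strict inequality in the body texts to ≤ 0.5 so that the count matches the modelled event and the titles. SAP section 5 and Tables 6.9.4.1 and 6.9.4.2 also use the strict form and should be checked in the same edit.
4. **Table 6.9.6.2:** correct the cross-reference to Table 6.9.6.1.

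The cost is SAP wording and table shells. No new data, models or analyses are needed.

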7.6 Study Conduct

7.6.1 Schedule of Observations

This PMOS will be a single-arm, multi-center, prospective cohort study.

Non-interventional studies are one of several methodical instruments to collect information on drugs available on the market. Their defining characteristic is the lack of influence on the relationship between individual physicians and patients in respect to determining indication as well as choice and conduct of the treatment, while at the same time allowing for the structured and systematic collection of treatment data (see also Section 6 “Rationale”). Adalimumab must not be prescribed for the purpose of including a patient in this PMOS.

Patients will be informed about the type of therapy, alternate therapies, and risks, and they have to provide informed consent before the start of adalimumab therapy. Before enrollment in the PMOS, the patients will be made anonymous. AbbVie GK will only receive access to anonymous data. AbbVie GK can only identify the patients via their patient number.

The documentation consists of patient self-assessments as well as assessments by the physician. The following table provides an overview of the study visits with corresponding study activities (Table 1 “Study Schedule”).

Table 1. Study Schedule

Activity	Visit (Week)					
	0	12	24	52	76	104*
Patient Background	✓					
Inclusion / Exclusion criteria	✓					
Previous RA therapies	✓					
Concomitant diseases and therapies	✓	✓	✓	✓	✓	✓
Current adalimumab therapy	✓	✓	✓	✓	✓	✓
Current RA therapies	✓	✓	✓	✓	✓	✓
Effectiveness						
• DAS28	✓	✓	✓	✓	✓	✓
• CDAI	✓	✓	✓	✓	✓	✓
• SDAI	✓	✓	✓	✓	✓	✓
• HAQ	✓	✓	✓	✓	✓	✓
• EQ-5D	✓	✓	✓	✓	✓	✓
• mTSS (X-rays of Hands and Feet)	✓			✓		✓
Adverse Events		✓	✓	✓	✓	✓

* Week 104 or last visit

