Presence of complication: others	Patients with the complication items applicable to the details of blood disorders [diabetes mellitus, gastrointestinal disorder, osteoporosis, malignant tumour, demyelinating disorders, collagen disorders (other than rheumatoid arthritis), others] should be handles as “present,” when there is no description in the presence of complications, it should be handled as “undescribed,” respectively, and others should be handled as “absent.”
Presence of a past history	When any of the details of the past history is evaluated as present, it should be handled as “present,” when it is described as no complication, it should be handled as “absent,” and when there is no description both in past history and the details, it should be handled as “undescribed.”

Name of data	Derivation and calculation methods
Presence of a history of allergy	If there is nothing applicable to a history of allergy, it should be handled as “undescribed.” In the details, if the patient is applicable to both “drugs” and “food,” it should be handled as “both.”
RA stage/progression	If there is no description in the RA stage/progression, it should be handles as “undescribed.”
Disabilities in RA	If there is no description in the RA disability index, it should be handles as “undescribed.”
Presence of concomitant drugs (At start date of Humira treatment)	If there is any drug administration on the date of initial Humira treatment, it should be handled as “present,” and others should be handled as “absent.”
Presence of concomitant drugs (During treatment with Humira)	If there is any drug administration during treatment with Humira, it should be handled as “present,” and others should be handled as “absent.” Administration during treatment with Humira refers to all administration cases not applicable to the followings. 
 • The completion date of treatment with a concomitant drug is prior to the date of initial Humira treatment • The start date of treatment with a concomitant drug is after the date of final Humira treatment
Concomitant drug: MTX (mg/week)	The dose of MTX during the period including the date of initial Humira treatment should be sorted into the following three categories: “ ≥ 12.0 mg/week and < 14.0 mg/week,” “ ≥ 14.0 mg/week and < 16.0 mg/week,” and “ ≥ 16.0 mg/week.”

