Purpose of analysis: Among the efficacy endpoints, DAS28-4CRP, DAS28-4ESR, CDAI, SDAI, HAQ-DI, and EQ-5D scores at the start of Humira treatment, the scores and the change at week 52, the scores and the change at week 104, and at the final evaluation should be read out with patient background information. Additionally, of the efficacy endpoints, mTSS score at each reading session of X-ray score should be indicated. The scores at the start of Humira treatment and week 52, and the change at week 52 at the first reading session should be shown as a list with the flag information that can identify the mTSS change at week 52 as additional information: ≤ 0 (No Progression), ≤ 0.5 (Structural Remission), ≥ 3.0 , and > 10.0 (Rapid Progression). When using the scores of the second reading session, the scores and the change at week 104 should be indicated in a list, and the flag information that can identify the change at 104 should be indicated as additional

information: ≤ 0 (No Progression), ≤ 0.5 (Structural Remission), ≥ 3.0 , and > 10.0 (Rapid Progression).

Note: This form should be prepared only at the time of literature analysis.

“8.2 List of Discontinuation of ADA Group by Questionnaire Part III”

Analysis object: Patients included in the efficacy analysis set (third CRF)

Purpose of analysis: To indicate the efficacy evaluation for the patients evaluated for efficacy in the third CRF as a list.

Note: None in particular.

14. Tabulation history

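### The SAP's only multivariable specification (mTSS change ≤0.5) omits baseline mTSS, baseline DAS28-4CRP and MTX dose at treatment start, all of which are collected

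*SAP*

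**What the plan says.** SAP 13.3, Table 6.9.6.1, fits a multivariable logistic regression with an mTSS change of 0.5 or less at week 52 as the outcome. On covariates it says "Gender (male, female)], [complication (absence, presence)] and [progression (Stage I/Stage II, Stage III/Stage IV)] should be handled as categorical data", and that "the results should be indicated as the quantitative data for [duration of illness" (written there in brackets as the fourth factor). That makes four terms, and no rule is given for choosing them. The table is marked for the literature analysis only. Table 6.9.6.2 repeats the model at week 104, but describes its method as "by using the same technique as Table 6.9.6.2", which is a reference to itself.

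The other baseline values are available:

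- **MTX dose.** The Spearman table for the same outcome (Table 6.9.4.1) lists "MTX at treatment start", and the univariate logistic models (Tables 6.2.6 and 6.9.5.1) include it. SAP 10.1 says "The dose of MTX during the period including the date of initial Humira treatment should be sorted into the following three categories". Table 7.1 also summarises the numeric dose.
- **Baseline DAS28-4CRP.** It is in the same univariate models, both in categories and as a continuous variable: "duration of illness] and [DAS28-4CRP at treatment start] as the quantitative data".
- **Baseline mTSS.** Protocol 7.6.1, Table 1, schedules "mTSS (X-rays of Hands and Feet" at weeks 0, 52 and 104. The SAP's listing 8.1 prints "The scores at the start of Humira treatment and week 52, and the change at week 52 at the first reading session". It is not among the patient background factors in SAP 11 or Table 6.9.4.1, and it is a covariate in no regression.

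**The concern.** The outcome is a change from baseline mTSS, yet the starting value is not in the model. RA stage and disease duration are plausibly related to damage and activity already present when adalimumab starts. If so, their odds ratios can carry part of the association that belongs to the omitted values. A reader of a publication would tend to take an odds ratio from the only adjusted model as an independent predictor.

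MTX dose raises a separate gap. The protocol's introduction and rationale cite earlier retrospective signals of better results at higher doses, and its synopsis promises regression on factors that influence effectiveness. In this non-interventional study physicians choose the dose, so unadjusted dose contrasts are open to confounding by severity. The one place where an adjusted dose estimate could have been given does not give it.

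**Working it through.** **1. The plan's own figure.** No precision or sample size is stated for this model. The only stated sample size is for the one-sample test of week-52 DAS28 remission (Protocol 13.1, SAP 4.3), with 42.7% against 55%, two-sided 0.05 and power 0.90:

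n = [1.960·√(0.427·0.573) + 1.282·√(0.55·0.45)]² / 0.123² = 170.7, rounded up to 171.

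With 50% dropout, 171/0.5 = 342, set at 350. The figure reproduces. It is used here only to anchor the number evaluable: 350 × 0.5 = 175.

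**2. Where each value is used.**

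| Baseline value | Univariate analyses | Multivariable model |
|---|---|---|
| Gender, complication, RA stage, disease duration | yes | yes |
| MTX dose at start | yes | no |
| DAS28-4CRP | yes | no |
| mTSS | no | no |

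Dose is otherwise examined by analysis of variance of DAS28-4CRP response across dose groups, with no covariates named (Tables 6.2.2, 6.2.4, 6.2.5), and in tabulations of serious adverse reactions by dose (Tables 5.2.3, 5.2.4). None of these is adjusted. DAS28 remission has a univariate model only (Table 6.2.6).

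**3. What omitting baseline mTSS could do.** This is an illustration on assumptions that are not in the documents. Stage III/IV has no effect of its own, 20% of patients are stage III/IV, and the probability of no progression is 70% at average baseline mTSS. Stage is linked to baseline mTSS through a latent correlation. A large simulated sample (400,000 records) gives these odds ratios for stage III/IV when baseline mTSS is left out:

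| Assumed OR per SD of baseline mTSS | correlation 0.2 | 0.4 | 0.6 |
|---|---|---|---|
| 0.7 | 0.89 | 0.79 | 0.70 |
| 0.5 | 0.80 | 0.65 | 0.52 |

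With baseline mTSS in the model the stage odds ratio returns to 1.00-1.01 in every case. This shows the mechanism and direction, not the size in this study.

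**4. What the fix costs.** Events per parameter = (number with the rarer outcome) / (number of covariate terms). Three continuous additions take the model from 4 to 7 terms. The number evaluable (175) and the proportion without progression are assumptions.

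| Without progression | Progressors | 4 terms | 7 terms |
|---|---|---|---|
| 60% | 175 × 0.40 = 70 | 17.5 | 10.0 |
| 75% | 175 × 0.25 = 43.75 | 10.9 | 6.3 |
| 80% | 175 × 0.20 = 35 | 8.8 | 5.0 |

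The relative fall is 1 − 4/7 = 43%. Entering MTX as three bands would use an eighth term (at 75%, 43.75/8 = 5.5).

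The number with readable X-rays is uncertain in both directions. At 60/70/80% without progression, seven terms give 5.7/4.3/2.9 events per parameter with 100 patients and 14.3/10.7/7.1 with 250. Protocol 7.6.2 records data only where assessed in routine care, and week 104 will probably have fewer films than week 52.

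**The case against.** A reader might infer that the model fails at the study's dose question. The documents do not support that. The objectives (Protocol 2.0 and 7.0) concern the effectiveness of adalimumab with MTX at or above 12 mg/week in a single arm. No passage gives Tables 6.9.6.1 and 6.9.6.2 the task of estimating a dose effect. Baseline dose lies in a narrow range by design, from the entry minimum of 12 mg/week to the approved maximum of 16 mg/week cited in the introduction. What stands is narrower: the SAP examines dose in several tables, and none is adjusted.

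A reader might also infer that the stage and duration odds ratios are shown to be biased. They are not. The documents give no correlation or effect size. RA stage is already in the model and may act as a coarse proxy for structural damage. Baseline damage may also lie on the path from disease duration to later progression, in which case adjusting for it changes the question asked. These points have force, but they are met by reporting the models with and without the additions.

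The sentence before the covariate list speaks of each background factor, so all factors might have been meant. The bracketed list is the operative one, as in the univariate tables. If it were not, the text would still need correcting, and baseline mTSS would still be absent because it is not a listed background factor.

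Finally, it might be said that three more terms cost little. A 43% fall in events per parameter is not negligible.

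**Conclusion.** The point holds as a specification gap in a secondary model. Its four covariates are unexplained, the starting value of its own outcome enters no regression, and the SAP contains no adjusted estimate for MTX dose. The stage and duration odds ratios may partly stand for baseline damage and activity. The simulated values in the working depend on assumed correlations and effects and should not be read as estimates for this study.

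The reach is limited. Table 6.9.6.1 is for the literature analysis, and Table 6.9.6.2 follows it. The week-52 DAS28 remission result does not depend on either. The change is worth making before the model is run, because it needs no new data, but it should not be presented as free.

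**What to change.** In Tables 6.9.6.1 and 6.9.6.2, add the following as single continuous terms, in this order of priority:

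1. Baseline mTSS, from the same reading session as the outcome: the first session for week 52 and the second for week 104. SAP 8 indicates that the second session also scores baseline films.
2. MTX dose at treatment start, in mg/week.
3. Baseline DAS28-4CRP. The continuous form is needed, because entry requires DAS28-CRP above 3.2 and the planned category below 2.6 should be almost empty.

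Keep the four-term model as a sensitivity analysis. State that penalised (Firth) logistic regression will be used if the rarer outcome gives fewer than about 10 events per parameter. Correct the reference in Table 6.9.6.2 so that it points to Table 6.9.6.1.

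The cost is SAP wording and wider intervals, more so at week 104. Few patients should be lost to missing covariates even though SAP 9.1 rules out imputation, because MTX dose and DAS28-CRP are entry criteria and the outcome cannot be computed without baseline mTSS. Any dose association would still be observational, over a narrow dose range, and should be reported as such.
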